5.3.4.2. Gastrointestinal Toxicity

Immune-mediated colitis has been associated with the administration of nivolumab. Diarrhea or colitis was reported in 21% of patients in two trials of nivolumab. Immune-mediated colitis occurred in 2.2% of patients in one trial- of these one patient had Grade 2 colitis, and five had Grade 3 colitis. In the other trial, Grade 3 immune-mediated colitis occurred in 0.9% of patients.

Patients should be advised to inform the investigator if any diarrhea occurs, even if it is mild. Range for time to onset of symptoms of colitis has been 1-6 months.

If the event is of significant duration or magnitude or is associated with signs of systemic inflammation or acute phase reactants (e.g. increased CRP or platelet count or bandemia), it is recommended that sigmoidoscopy (or colonoscopy, if appropriate) with colonic biopsy with three to five specimens for standard paraffin block be performed.

Treatment may be restarted following the resolution of colitis. In addition, if the patient is being managed with corticosteroids, treatment should not be restarted until the steroids have been tapered down to a prednisone dose \leq 10 mg/day. Patients who resume treatment should be monitored closely for signs of renewed diarrhea.

Table 2 provides a summary of dose modification guidelines for gastrointestinal toxicities.

Table 2 Dose Modification Guidelines for Gastrointestinal Toxicity

Symptoms	Management	Follow-up
Grade 1 diarrhea: <4 stools per day over baseline Grade 1 colitis: asymptomatic colitis	Continue nivolumab Administer symptomatic treatment	
 - Close monitoring for worsening symptoms - Educate patients to report worsening immediately
Grade 2 diarrhea: 4-6 stools per day over baseline 
 - IV fluids indicated <24 hrs - Not interfering with ADL Grade 2 Colitis: abdominal pain, blood in stool	Withhold nivolumab Administer symptomatic treatment If symptoms persist >5 days or recur: 0.5 to 1 mg/kg/day prednisone equivalents	
If improved:
 
 - resume nivolumab - if steroids have been administered, taper steroids over at least 1 month before resuming nivolumab 
If symptoms worsen or persist >3-5 days with oral steroids:
 
 - treat as Grade 3 or 4
Grade 3 or 4 Grade 3 diarrhea: ≥ 7 stools per day over baseline, incontinence 
 - IV fluids ≥ 24 hs - Interferes with ADLs Colitis Grade 3: severe abdominal pain, medical intervention indicated, peritoneal signs present Colitis Grade 4: life threatening symptoms, perforation	Grade 3: withhold nivolumab until symptoms are Grade 1 Grade 3 persists or worsens, or Grade 4: permanently discontinue nivolumab Administer 1-2 mg/kg/day prednisone equivalents Consider lower-GI endoscopy	
If improved from Grade 3:
 
 - when at Grade 1, taper steroids over 1 month before resuming nivolumab 
If improved from persistent Grade 3 or Grade 4
 
 - continue steroids until Grade 1, then taper over at least 1 month 
If symptoms persist >3-5 days, or recur after improvement
 
 - add non-corticosteroid immunosuppressive medication

5.3.4.3. Hepatotoxicity

Immune-mediated hepatitis has occurred with the administration of nivolumab.

Patients should be monitored for abnormal liver tests prior to and periodically during treatment. While on this study, patients presenting with right upper-quadrant abdominal pain and/or unexplained nausea or vomiting should have LFTs performed immediately and LFTs should be reviewed before administration of the next dose of study drug.

If LFTs increase, neoplastic, concurrent medications, viral hepatitis, and toxic etiologies should be considered and addressed, as appropriate. Imaging of the liver, gall bladder, and biliary tree should be performed to rule out neoplastic or other causes for the increased LFTs. Anti-nuclear antibody, perinuclear anti-neutrophil cytoplasmic antibody, anti-liver-kidney microsomal antibodies, and anti-smooth muscle antibody tests should be performed in an autoimmune etiology is considered.

Patients with LFT abnormalities should be managed according to the guidelines in Table 3.

Table 3 Dose Modification Guidelines for Hepatotoxicity

Symptoms	Management	Follow-up
Grade 1: AST or ALT >ULN to 3xULN and/or T Bili >ULN to 1.5xULN	Continue nivolumab Regularly monitor LFTs	Continue monitoring LFTs
Grade 2: AST or ALT >3 to \leq 5 x ULN and/or T Bili >1.5 to \leq 3 ULN	
 - Withhold nivolumab - Increase frequency of monitoring to every 3 days - 1 to 2 mg/kg/day prednisone equivalents 	If improved to Grade 1 or baseline, resume nivolumab. If steroids have been administered, taper steroids over at least 1 month before resuming nivolumab. Resume routine LFT monitoring
Grade 3 or 4: AST or ALT >5x ULN and/or T Bili >3x ULN	
 - Permanently discontinue nivolumab - Increase frequency of monitoring to every 1-2 days - Gastroenterology consult - Treat with 1-2 mg/kg/day prednisone equivalent 	If improved to <Grade 2, taper steroids over at least 1 month If labs persist >3-5 days, worsen or rebound: add non-corticosteroid immunosuppressive medication

IV = intravenous; LFT = liver function test; ULN = upper limit of normal.

5.3.4.4. Renal Toxicity

Immune-mediated nephritis or renal dysfunction occurred with nivolumab treatment. Patients should be monitored for elevated serum creatinine prior to and periodically during treatment and clinically monitored for symptoms of decreased volume of urination, hematuria, peripheral edema, and loss of appetite.

In one trial, there was increased incidence of elevated creatinine in the nivolumab-treated group as compared to chemotherapy (13% v 9%). Grade 2 or 3 immune-mediated nephritis or renal dysfunction occurred in 0.7% (2/268) of patients. In another trial, the incidence of elevated creatinine was 22%, with Grade 2 immune-mediated renal dysfunction occurring in 0.9% (1/117) patients.

Renal toxicity should be managed according to the guidelines in Table 4.

Table 4 Dose Modification Guidelines for Renal Toxicity

Toxicity, Grade	Management	Follow-up
Grade 1 - Creatinine >ULN and >baseline but \leq 1.5x baseline	Continue nivolumab - Monitor creatinine weekly	If improved to baseline, resume routine creatinine monitoring.
Grade 2 or 3 - Creatinine >1.5 to \leq 6x ULN or >1.5 x baseline	Withhold nivolumab - Monitor creatinine every 2-3 days - Treat with 0.5 to 1 mg/kg/day prednisone equivalents - Consider renal biopsy	If improved to Grade 1, taper steroids over at least 1 month before resuming nivolumab with routine creatinine monitoring. If elevations persist >7 days or worsen, treat as Grade 4
Grade 4 - Creatinine >6x ULN	Permanently discontinue nivolumab - Monitor creatinine daily - Nephrology consult - Treat with 1-2 mg/kg/day prednisone equivalents - Consider renal biopsy	If improved to Grade 1, taper steroids over at least 1 month

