5.3.1.4. Dose Modification for Adverse Reactions

The dose of study drug should be modified according to the dose modification guidelines in Table 1 if any of the following toxicities occur:

- Grade 4 ANC (<500/ μ L) for more than 7 days or fibroneutropenia.
- Grade 3 thrombocytopenia (<50,000/ μ L) in the presence of clinically significant bleeding events.
- Grade 4 thrombocytopenia (<25,000/ μ L).
- Grade 3 or 4 nausea, vomiting, or diarrhea if persistent, despite optimal anti-emetic and/or anti-diarrheal therapy.
- Any other Grade 4 or unmanageable Grade 3 toxicity.

For Grade 3 or 4 atrial fibrillation or persistent atrial fibrillation of any grade, consider the risks and benefits of ibrutinib treatment. If clinically indicated, the use of anticoagulants or antiplatelet agents may be considered for the thromboprophylaxis of atrial fibrillation (Section 6.2.4).

Note: After a dose reduction, dose escalation of ibrutinib to a previous higher dose is NOT allowed.

Table 1. Ibrutinib Dose Modifications

Occurrence	Action to be Taken
First	Withhold study drug until recovery to Grade ≤ 1 or baseline; may restart at original dose level
Second	Withhold study drug until recovery to Grade ≤ 1 or baseline; may restart at 1 dose level lower (ie, 280 mg/day for 420 mg/day dose; 420 mg/day for 560 mg /day dose)
Third	Withhold study drug until recovery to Grade ≤ 1 or baseline; may restart at 1 dose level lower (ie, 140 mg/day for 420 mg/day dose; 280 mg/day for 560 mg /day dose)
Fourth	Discontinue study drug

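### Table 4 (renal toxicity) gives conflicting nivolumab instructions when baseline creatinine is above ULN, and above 1.5 x ULN its exit rule does not recognise recovery to baseline

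*Combined protocol and SAP*

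**What the plan says.** Section 5.3.4.4 directs that renal toxicity be managed by Table 4. Three parts of the table matter here.

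- **Grade 1 row:** "Creatinine >ULN and >baseline but" no more than 1.5 x baseline. Nivolumab continues, with weekly creatinine. The follow-up entry reads "If improved to baseline, resume routine creatinine monitoring".
- **Grade 2 or 3 row:** creatinine above 1.5 and up to "6x ULN or >1.5 x baseline". Nivolumab is withheld and prednisone or equivalent is given at 0.5 to 1 mg/kg/day.
- **Leaving the Grade 2 or 3 row:** "If improved to Grade 1, taper steroids over at least 1 month before resuming nivolumab with routine creatinine monitoring". Otherwise, "If elevations persist >7 days or worsen, treat as Grade 4", and Grade 4 handling is permanent discontinuation.

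Two sister tables have a wider exit. The ibrutinib rule in Table 1 allows restart on recovery to Grade 1 or lower "or baseline; may restart at original dose level". The hepatic rule in Table 3 says "If improved to Grade 1 or baseline, resume nivolumab".

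For renal function, section 4.1 asks only for an estimated clearance of at least 30 ml/min (Cockcroft-Gault).

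**The concern.** The Grade 1 row is capped relative to the patient's own baseline. The Grade 2 or 3 row can be entered through ULN alone, because its two limbs are joined by *or*. The two scales agree while baseline is at or below ULN and come apart once it is higher. The liver criteria are better protected: section 4.1 caps AST/ALT at 3 x ULN and bilirubin at 1.5 x ULN (with an exception for Gilbert's syndrome or non-hepatic causes), and these are Table 3's Grade 1 ceilings. Creatinine has no such cap.

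At stake is how an individual patient is treated. The same small rise leads either to weekly monitoring, or to a hold, systemic steroids and a taper of at least a month before resumption. With dosing every 2 weeks, a 4-week taper alone costs at least 4/2 = 2 of the 26/2 = 13 doses due in 26 weeks. Creatinine rises are not rare: section 5.3.4.4 cites 13% and 22% in two nivolumab trials. It reports immune-mediated renal dysfunction of Grade 2 or 3 in 0.7% of one trial and of Grade 2 in 0.9% of the other.

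**Working it through.** The plan gives no figure of its own on this point, so the check is of the table's logic, followed by whether eligible patients can reach the conflict.

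**Step 1. Code the rows.** Let *b* be baseline and *c* the current creatinine, both in multiples of ULN.

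- Grade 1: *c* > 1, *c* > *b* and *c* ≤ 1.5*b*.
- Grade 2 or 3: 1.5 < *c* ≤ 6, or *c* > 1.5*b*.

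For *b* up to 4, both rows hold when max(*b*, 1.5) < *c* ≤ 1.5*b*. The interval is empty for *b* ≤ 1 and non-empty for *b* > 1.

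| Baseline (x ULN) | Values in both rows (x ULN) | Row met at an unchanged baseline |
|---|---|---|
| 1.0 | none | none |
| 1.1 | above 1.5 to 1.65 | none |
| 1.3 | above 1.5 to 1.95 | none |
| 1.5 | above 1.5 to 2.25 | none |
| 1.8 | above 1.8 to 2.7 | Grade 2 or 3 |
| 2.0 | above 2.0 to 3.0 | Grade 2 or 3 |

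**Step 2. Look at recovery.** Grade 1 requires a value above baseline, so a value at baseline is never Grade 1. If *b* ≤ 1.5, a return to baseline meets no row and is naturally read as better than Grade 1. If *b* > 1.5, the same value still meets the withhold row through the ULN limb. The exit condition is then not literally met on full recovery.

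**Step 3. Check eligibility.** The highest creatinine allowed at a clearance of 30 ml/min is (140 − age) x weight / (72 x 30) for a man. Age, weight and ULN are assumptions; ULN is taken as 1.2 to 1.3 mg/dL for men.

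- Age 65, 80 kg: 75 x 80 / 2160 = 2.78 mg/dL, or 2.14 to 2.31 x ULN. Both problems can arise.
- Age 75, 60 kg: 65 x 60 / 2160 = 1.81 mg/dL, or 1.39 to 1.50 x ULN. Essentially only the row conflict can arise.

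**Step 4. Worked patient.** The 65-year-old enters at 2.0 mg/dL, with clearance 6000/(72 x 2.0) = 41.7 ml/min. He rises to 2.2 mg/dL, with clearance 6000/(72 x 2.2) = 37.9 ml/min.

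- Against baseline: 2.2/2.0 = 1.10, so Grade 1 and continue.
- Against ULN: 2.2/1.3 = 1.69 to 2.2/1.2 = 1.83, so Grade 2 or 3 and withhold with steroids.
- Back at 2.0 mg/dL: 2.0/1.3 = 1.54 to 2.0/1.2 = 1.67 x ULN, which still meets the withhold row.

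**The case against.** The best defence is that these tables are guidelines. Sections 5.3.3 and 5.3.4 place them under standard medical practice, and 5.3.3 adds investigator benefit/risk judgement and the prescribing information. Section 5.3.3 also gives a default for Grade 1-2 immune-related events: supportive care with nivolumab continued. That permits a sensible choice but does not say which row applies. Table 4 is more specific and departs from the default by withholding at Grade 2, so the conflict stands.

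A reader might infer that a patient with a high baseline must be permanently discontinued after 7 days. The documents do not support that as the only reading. Table 4's Grade 1 follow-up treats baseline as better than Grade 1. Section 5.3.4 ties suspension to toxicity considered related to the study drug. Section 11.1.1 does not count an unworsened pre-existing condition as an adverse event. A creatinine back at baseline is not naturally a persisting elevation. This part of the objection largely stands: what remains is a literal gap in the exit rule, confined to baselines above 1.5 x ULN.

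A reader might also note that the limb based on 1.5 x baseline has no ceiling, so it can hold alongside the Grade 4 criterion, "Creatinine >6x ULN". This is not worth pursuing. Only one row carries the Grade 4 label, and the Grade 2 or 3 row itself sends worsening values to Grade 4 handling.

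**Conclusion.** Table 4 is wrong as written, at a minor level. For any eligible baseline above ULN it gives two incompatible instructions over a definable range of creatinine, with no precedence rule. For a baseline above 1.5 x ULN its exit wording also fails to recognise full recovery. The logic of both follows from the documents alone. That patients can reach the conflict rests on the assumed ages, weights and ULN, but section 4.1 has no creatinine cap that would prevent it.

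The documents give no baseline renal distribution, so the number affected among 30 is unknown and may be near zero. It would be wrong to infer any effect on the design: the sample size and the 15-of-25 criterion do not depend on Table 4.

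**What to change.** Change the wording of Table 4 as follows.

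- (a) State that a creatinine at or below the patient's own baseline is not a Table 4 toxicity.
- (b) Add *or baseline* to both entries that depend on improvement to Grade 1 (the Grade 2 or 3 row and the Grade 4 row).
- (c) State that the 7-day escalation stops once creatinine is back to Grade 1 or baseline.
- (d) Name one row for rises above baseline that meet both rows.

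The choice in (d) is clinical and belongs to the sponsor. If the more severe row governs, (a) is essential. Without it, a patient with a baseline above 1.5 x ULN meets the withhold row before any rise, and would meet it again on resuming at baseline. Even with (a), that choice means holds and steroids for small rises in patients with high baselines, such as the 10% rise in the worked patient. If the milder row governs, he could continue up to 1.5 x 2.0 = 3.0 mg/dL. His clearance would then be 6000/(72 x 3.0) = 27.8 ml/min, below the entry floor of 30.

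The cost is an amendment to one table. No test, visit or eligibility criterion changes.

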5.3.4.5. Endocrine Toxicity

Immune-mediated hypothyroidism and hyperthyroidism has been associated with the administration of nivolumab. In one trial, Grade 1 or 2 hypothyroidism occurred in 8% (21/268) of patients receiving nivolumab. Grade 1 or 2 hyperthyroidism occurred in 3% (8/268) of patients on nivolumab on that trial, and in 1% (1/102) patients receiving chemotherapy. In another trial, hypothyroidism occurred in 4.3% (5/117) of patients. Hyperthyroidism occurred in 1.7% (2/117) of patients. One patient experienced Grade 2 hyperthyroidism.

Patients with unexplained symptoms such as fatigue, headaches, myalgias, impotence, mental status changes, or constipation should be investigated for the presence of thyroid, pituitary, or adrenal endocrinopathies, as well as for hyponatremia or hyperkalemia. An endocrinologist should be consulted if an endocrinopathy is suspected. TSH and free T4 levels should be obtained to determine if thyroid abnormalities are present. TSH, prolactin, and a morning cortisol level will help to differentiate primary adrenal insufficiency from primary pituitary insufficiency.

Hypothyroidism should be managed according to the guidelines in Table 5.

Table 5 Dose Modification Guidelines for Endocrine Toxicity

Toxicity Grade	Management	Follow-up
Asymptomatic endocrinopathy (e.g hypothyroidism or hyperthyroidism)	
 - Continue nivolumab - If TSH <0.5 xLLN or TSH >2x ULN, or consistently out of range in 2 subsequent measurements, include free T4 at subsequent cycles as clinically indicated - Consider endocrinology consult 	Continue standard monitoring
Symptomatic endocrinopathy – either hypothyroidism or hyperthyroidism	
 - continue nivolumab for hypothyroidism or hyperthyroidism - withhold nivolumab for other endocrinopathies with abnormal lab/pituitary scan - evaluate endocrine function - consider pituitary scan - repeat labs in 1-3 weeks - repeat MRI in 1 month if symptoms persist but normal lab/pituitary scan - consider endocrinology consult 	If improved (with or without hormone replacement)- resume nivolumab Continue standard monitoring Patients with adrenal insufficiency may need to continue steroids with mineralocorticoid component
Suspicion of adrenal crisis: 
 - severe dehydration - hypotension - shock out of proportion to current illness 	
 - withhold nivolumab - rule out sepsis - consult endocrinology - stress-dose IV steroids with mineralocorticoid activity (may be switched to an equivalent dose of oral corticosteroids at start of tapering or earlier, once sustained clinical improvement observed) - administer IV fluids 	When adrenal crisis ruled out, treat as symptomatic endocrinopathy

TSH = thyroid-stimulating hormone.

5.3.4.6. Pulmonary Toxicity

Severe pneumonitis or interstitial lung disease, including fatal cases, have occurred with nivolumab treatment. As such, patients must be monitored for signs and symptoms of pneumonitis. Across clinical trial experience in 691 patients with solid tumors, fatal immune mediated pneumonitis occurred in 0.7% (5/691) of patients receiving nivolumab. In one trial 2.2% (6/268) of patients receiving nivolumab developed immune-mediated pneumonitis, one with Grade 3 and with Grade 2 cases. In another trial, immune-mediated pneumonitis occurred in 6% (7/117) of patients receiving nivolumab including five Grade 3 and two Grade 2 cases.

Pulmonary toxicity should be managed according to the guidelines in Table 6.

Table 6 Dose Modification Guidelines for Pulmonary Toxicity

Description	Management	Follow-up
Grade I- radiographic changes only	
 - Consider withholding nivolumab. - Monitor every 2-3 days - consider pulmonary and infectious disease consults. 	
 - Reassess at least every 3 weeks - If improved, resume nivolumab (if it has been discontinued) when symptoms stabilized - If worsens, treat as Grade 2 or above
Grade 2: 
 - mild to moderate symptoms - radiographic changes 	
 - withhold nivolumab - monitor daily - consult Pulmonary and Infectious diseases - treatment with 1 mg/kg/day prednisone or equiv - consider bronchoscopy/lung biopsy 	If improved to baseline: 
 - taper steroids over at least 1 month before resuming nivolumab If not improving after 2 weeks or worsening: 
 - treat as Grade 3 or 4
Grade 3 or 4: 
 - severe symptoms - new/worsening hypoxia - life-threatening symptoms 	
 - Hospitalize patient - Permanently discontinue nivolumab - Monitor daily - Obtain Pulmonary and Infectious Disease consults - Treat with 1-2 mg/kg/day prednisone or equivalent - Consider bronchoscopy, lung biopsy 	If improved to baseline: 
 - taper steroids over at least 1 month If persists or worsens after 2 days 
 - add non-corticosteroid immunosuppressive medication

5.3.4.7. Pericardial and Pleural Effusions

Pericardial and pleural involvement with associated effusions is common in patients with NSCLC and have the theoretical potential to be exacerbated by inflammation associated with antitumor immunity following PD-L1 blockade. Patients presenting with dyspnea, chest pain, or unexplained tachycardia should be evaluated for the presence of a pericardial effusion. Patients with preexisting pericardial effusion should be followed closely for pericardial fluid volume measurements and impact on cardiac function. When intervention is required for pericardial or pleural effusions, appropriate workup includes cytology, LDH, glucose, cholesterol, protein concentrations (with pleural effusions), and cell count. For patients with a pericardial effusion causing end-diastolic right ventricular collapse, treatment may be restarted following the placement of a pericardial window, demonstrations of hemodynamic stability, and resolution of right ventricular dysfunction.

6. CONCOMITANT MEDICATIONS/PROCEDURES

6.1. Permitted Concomitant Medications

Supportive medications in accordance with standard practice (such as for emesis, diarrhea, etc.) are permitted. Use of neutrophil growth factors (filgrastim and pegfilgrastim) or red blood cell growth factors (erythropoietin) is permitted per institutional policy and in accordance with the ASCO guidelines (Smith 2006). Transfusions may be given in accordance with institutional policy.

Short courses (≤ 14 days) of steroid treatment for non-cancer related medical reasons (eg, joint inflammation, asthma exacerbation, rash, antiemetic use and infusion reactions) at doses that do not exceed 100mg per day of prednisone or equivalent are permitted.

6.2. Medications to be Used with Caution

6.2.1. CYP3A- Inhibitors/Inducers

Ibrutinib is metabolized primarily by CYP3A. Avoid co-administration with strong CYP3A inhibitor (eg, ketoconazole, indinavir, nelfinavir, ritonavir, saquinavir, clarithromycin, telithromycin, itraconazole, cobicistat, posaconazole, and nefazadone) or moderate CYP3A inhibitors and consider alternative agents with less CYP3A inhibition. If a strong CYP3A inhibitor must be used, either reduce ibrutinib dose to 140 mg or withhold treatment temporarily (for 7 days or less). Subjects should be monitored for signs of ibrutinib toxicity. If a moderate CYP3A inhibitor (eg. Fluconazole, voriconazole, erythromycin, amprenavir, aprepitant, atazanavir, ciprofloxacin, crizotinib, diltiazem, fosamprenavir, imatinib, verapamil, amiodarone, and dronedarone) must be used, reduce ibrutinib to 140mg for the duration of the inhibitor use. No dose adjustment is required in combination with mild inhibitors. Avoid grapefruit and Seville oranges during ibrutinib treatment, as these contain moderate inhibitors of CYP3A (see Section 5.3.1.2).

Avoid concomitant use of strong CYP3A inducers (eg, carbamazepine, rifampin, phenytoin, and St. John's Wort). Consider alternative agents with less CYP3A induction.

A list of common CYP3A inhibitors and inducers is provided in Appendix 3. A comprehensive list of inhibitors, inducers, and substrates may be found at
<http://medicine.iupui.edu/clipharm/ddis/main-table/>

This website is continually revised and should be checked frequently for updates.

